1. PROTOCOL INFORMATION

Study Title: Efficacy of Eco-Friendly Toothpaste Tablets versus Conventional

Toothpaste using PI and GI Index

Funding Source: Loma Linda School of Dentistry

Investigation Product: Colgate "Cavity Protection" toothpaste and Colgate toothpaste

tablets

IND / IDE number: N/A Phase of Study: N/A

Version Date of Protocol: October 5, 2022

3. STUDY PERSONNEL INFORMATION

[name], Senior Dental Hygiene student [name], Senior Dental Hygiene student [name], Senior Dental Hygiene student [name], Senior Dental Hygiene student [name], Senior Dental Hygiene student [name], Senior Dental Hygiene student [name], Dental hygiene faculty

[contact]

Email Address: [contact]

4. STUDY INFORMATION

Location(s) of Research Activity: Loma Linda School of Dentistry Expected Start/Stop Dates of Research: 11/01/2022 to 08/30/2023

Special Time Sensitivities: N/A
Type of Research: *Minimal Risk*Anticipated Enrollment number: 40
Patient Population: 40 subjects

5. OBJECTIVES AND PURPOSE

Due to its travel-friendly size and eco-friendliness, toothpaste tablets have gained popularity among the green people. Green people are those who aim to achieve sustainability. Despite toothpaste tablets' many merits, there is only scarce information on the efficacy, consumer satisfaction, cost, and benefits. Therefore, the purpose of our study is to evaluate the efficacy of toothpaste tablets when compared to conventional toothpaste in removing plaque. We aim to evaluate this by, measuring gingival index (GI) and the plaque index (PI) on subjects that have been either using the tabs or toothpaste.

We hypothesize that there will be no statistically significant difference in GI and PI scores between the two groups. The results of the study will be highly significant as it will serve as a strong piece of evidence to recommend or not to recommend this newly developed product that has the potential to keep our planet safe from non-degradable plastic.

6. STUDY DESIGN

Background Information & Rationale

Countless plastic toothpaste tubes are thrown out daily because conventional toothpaste is the prime tooth cleansing agent for millions around the world. Despite its ability to effectively tackle gum disease, malodor (bad breath), calculus, and dentin hypersensitivity, populations are not utilizing the whole tube as 10% still remains when discarded. Therefore, plastic alternatives such as Colgate's Anywhere Toothpaste Tabs, DentTabs, Bite, and many other companies manufactured dissolving, chewable toothpaste in the form of small tablets. This favors sustainable consumerism at a slightly higher cost. Containing fewer ingredients than most toothpaste while packaged into reusable jars, toothpaste tablets' purpose forces individuals to be eco-friendly while still demonstrating excellent oral hygiene care. In addition, previous research has shown toothpaste tablets to have only a negligible dentin abrasion depth of 0.02mm compared to conventional toothpaste's 0.06mm loss. Regardless of its non-abrasive component and versatile size, the last several years prompted questions regarding tablets' capability of plaque elimination.

Plaque accumulates on tooth surfaces due to the presence of biofilm. Biofilm consists of bacterial microorganisms that start as translucent, unstructured film that can eventually transition into calcified hard tenacious stones inside the oral cavity. Due to its quick formation in a matter of 21 days, untouched biofilm left on tooth surfaces can ultimately lead to the development of dental caries and periodontal disease.

In order to show the effectiveness of plaque removal between conventional toothpaste versus toothpaste tablets, two highly recognized indices will be used: gingival index (GI) and Turesky's Modified plaque index (PI)—originally changed from Quigley Hein Index.

Gingival Index (GI) was introduced by Loe and Silness in 1963. GI can be used in all teeth or selected teeth. The examination will be done by a blunt probe. The following teeth will be used,

The GI scores will indicate as follows,

0: No inflammation.

1: Mild inflammation, slight change in color, slight edema, no bleeding on probing.

2: Moderate inflammation, moderate glazing, redness, bleeding on probing.

3: Severe inflammation, marked redness and hypertrophy, ulceration, tendency to spontaneous bleeding.

The GI index will be calculated as follows,

GI Index= GI total scores/No of surfaces (N=18)

GI Index Interpretation,

0.1–1.0: Mild gingivitis

1.1–2.0: Moderate gingivitis

2.1–3.0: Severe gingivitis

For measuring plaque accumulation, the Turesky Modified version contains a basis from 0-5, while also distinguishing severity and location. The same six teeth will be used.

The PI scores will indicate as follows,

0: No plaque.

[figure not shown]
1: Separate flecks of plaque at the cervical margin of the tooth.

2: A thin continuous band of plaque at the cervical margin of the tooth.

3: A band of plaque wider than 1 mm covering less than 1/3rd of the crown of the tooth.

4: Plaque covering at least $1/3^{rd}$ but less than $2/3^{rd}$ of the crown of the tooth.

5: Plaque covering $2/3^{rd}$ or more of the crown of the tooth.

Given the environmental advantages of toothpaste tabs, it is worth exploring the effectiveness of tabs following the action of daily brushing within a 2-week trial period.

After measurements are recorded, comparison of the GI & PI results between tabs and conventional toothpaste will be assessed.

a. Endpoints

Primary endpoints

GI and PI scores between the use of dental tablets and conventional toothpaste.

Secondary endpoints

Satisfaction on user-friendliness of both types of toothpastes.

b. Overall study design

A convenience sample of 40 participants will be randomized into two groups containing 20 individuals each. Randomization will be performed by using a randomization table that is generated by the statistician. Selection of participants will concur to a written consent primarily based on voluntary agreement restricted only to a student consensus.

Group A. Colgate Cavity Protection will be selected as the conventional toothpaste for the control group due to its low abrasivity⁸.

Group B. Colgate Anywhere Toothpaste Tablets will be used as the prime cleansing agent for the experimental group.

Subjects will be instructed to use their normal oral hygiene routine throughout a 2-week timeline. New toothbrushes will be used for both groups—Colgate Slim Soft Gliding Tips Toothbrush, Extra Soft, Compact Head.

Group B will be instructed to use Colgate Anywhere toothpaste tablets where one tablet will be used for brushing. Subjects will gently chew on the tablet to dissolve it and will brush for two minutes at least twice a day. Any residual excess from the tablets are to be spit out. Group A will use Colgate Cavity Protection toothpaste and brush at least twice a day for two minutes.

c. Study Procedures and Schedule

Subjects will consent to participate. The examiner will then perform an oral examination to provide an evaluation of plaque and gingival **indexes**. Post 2 weeks, a final assessment will be given by the same examiner done in the exact order and technique as the baseline test. The teeth will be reevaluated with new numeric data, where the scores will be added then divided by the total site surfaces. At the end participants will receive a 10-item satisfaction survey.

- d. Alternative procedures \rightarrow N/A
- e. Deception \rightarrow N/A
- f. Investigational New Drug (IND) \rightarrow N/A

7. INCLUSION / EXCLUSION CRITERIA

Inclusion criteria:

- 1. Subjects are 18 years or older;
- 2. Subjects who will comply with study protocol;
- 3. Subjects who can read and understand the consent form;
- 4. Subjects available during the study period;
- 5. Subjects have more than 20 teeth.

Exclusion criteria:

- 1. Subjects who are pregnant and/or nursing;
- 2. Subjects under the age of 18.

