17. STATISTICAL ANALYSIS

We hypothesize that there will be no statistically significant difference in GI and PI scores between the two groups. To test this hypothesis, we will use an independent sample t-test to compare the difference in GI and PI scores between the two groups. If it is determined that GI and/or PI are not normally distributed, we will proceed with testing our hypothesis with the Mann-Whitney U-test. This hypothesis will be tested at an alpha level of 0.05 and will be two-sided. A sample size analysis was conducted and demonstrated that 20 samples per group were necessary to achieve 80% power to test this hypothesis at an alpha level of 0.05.

18. DATA AND SAFETY MONITORING PLAN (DSMP)

N/A

19. LITERATURE REFERENCES

- 1. Gängler, Peter et al. "In vitro effect of fluoride oral hygiene tablets on artificial caries lesion formation and remineralization in human enamel." *BMC oral health* vol. 9 25. 2 Oct. 2009, doi:10.1186/1472-6831-9-25
- 2. Shaikh, Mohammed et al. "Micro computed tomography analysis of abrasivity of toothpaste tablets compared to conventional toothpaste." *American journal of dentistry* vol. 34,5 (2021): 235-239.
- 4. Chasma, Farida, and Gary Cousin. "Keeping Teeth Clean but Not at the Environment's Expense." *Faculty Dental Journal*, vol. 12, no. 1, 2021, pp. 20–22., https://doi.org/10.1308/rcsfdj.2021.5. https://www.researchgate.net/publication/348155830 Keeping teeth clean but not at the environment's expense
- 5. Moslehzadeh, Kaban. "Quigely Hein Index (modified). *Malmo University*. 27 Apr. 2016, https://www.mah.se/CAPP/Methods-and-Indices/Oral-Hygiene-Indices/Quigely-Hein-Index-modified/
- 6. Lippert F. An introduction to toothpaste its purpose, history and ingredients. *Monogr Oral Sci* 2013; 23:1-14.
- 7. 300 million toothpaste tubes go to landfill. *Br Dent J* 2021; 230-390.

- 8. Löe H. The Gingival Index, the Plaque Index and the Retention Index Systems. J Periodontol. 1967 Nov-Dec;38(6):Suppl:610-6. doi: 10.1902/jop.1967.38.6.610. PMID: 5237684.
- https://aap.onlinelibrary.wiley.com/doi/abs/10.1902/jop.1967.38.6.610?sid=nlm%3Apubmed

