Gingivitis	Toothpaste Tablet	20	-0.026	1.9	0.765	-0.117	0.064
	Conventional Dentifrice	20	-0.011	0.8	0.936	-0.070	0.048
Plaque	Toothpaste Tablet	20	-0.224	8.0	0.017	-0.453	0.005
	Conventional Dentifrice	20	-0.218	7.8	0.035	-0.391	-0.045

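### GI is a primary endpoint at two weeks without a rationale that it would respond; with no margin and 20 per arm, a non-significant GI difference is weak evidence of equal efficacy

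*Combined protocol and SAP*

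**What the plan says.** - **Purpose (Section 5).** The study is to "evaluate the efficacy of toothpaste tablets when compared to conventional toothpaste in removing plaque". Its results are meant to serve as strong evidence for or against recommending tablets.
- **Indices (Section 6).** GI grades inflammation from none, through redness and bleeding, to ulceration. PI (Turesky modification) grades how much of the crown carries plaque.
- **Primary endpoints (Section 6a).** "GI and PI scores between the use of dental tablets and conventional toothpaste". Both indices have the same status.
- **Timing (Section 6, Section 6c, Schedule of Events).** The rationale is that "it is worth exploring the effectiveness of tabs following the action of daily brushing within a 2-week trial period". After baseline there is one more examination: "Post 2 weeks, a final assessment will be given by the same examiner". No sentence links two weeks to the time GI needs to change.
- **Conditions (Sections 6b and 7).** Subjects keep their normal hygiene routine, brush at least twice daily for two minutes, and receive the same new brush in both arms. No minimum GI is required for entry.
- **Analysis (Section 17).** "We hypothesize that there will be no statistically significant difference in GI and PI scores between the two groups". The test is a two-sided t-test (or Mann-Whitney) at 0.05. There is no equivalence or non-inferiority margin. Twenty per group is said to give 80% power, but the endpoint, effect size and SD are not named.

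**The concern.** The hoped-for conclusion is an absence of difference, and Section 12 expects that finding to encourage a switch to tablets. Such a conclusion is only as good as the endpoint's ability to show a difference had there been one. For GI the plan gives no ground to expect movement in two weeks, and no size of difference that would matter. If GI barely moves in either arm, the test will usually be non-significant whether or not the tablet does what the toothpaste does. As written, the plan would still count that result as half of its primary evidence, for an objective (plaque) that GI does not measure.

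**Working it through.** **Inputs.** Baseline means and SDs come from Table 2, two-week means and SDs from Table 3, and within-arm changes with 95% CIs from Table 4. There are 20 subjects per arm. Differences are tablet minus toothpaste, and a higher score is worse.

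**1. The plan's own figure.** The 20 per group cannot be reproduced, because no effect size or SD is stated. Solved backwards, the detectable standardised difference is (1.960 + 0.842) x sqrt(2/20) = 0.89 by the normal approximation, or 0.91 with the t distribution. The pooled two-week GI SD is sqrt((0.26² + 0.18²)/2) = 0.224. The detectable difference is 0.909 x 0.224 = 0.20 GI units.

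**2. How far each index moved.**

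| Index, arm | Change (Table 4) | 95% CI | % of baseline | Baseline SDs |
|---|---|---|---|---|
| GI, tablet | -0.026 | -0.117 to 0.064 | 0.026/1.35 = 1.9% | 0.026/0.26 = 0.10 |
| GI, toothpaste | -0.011 | -0.070 to 0.048 | 0.011/1.37 = 0.8% | 0.011/0.24 = 0.05 |
| PI, tablet | -0.224 | -0.453 to 0.005 | 0.224/2.80 = 8.0% | 0.224/0.58 = 0.39 |
| PI, toothpaste | -0.218 | -0.391 to -0.045 | 0.218/2.78 = 7.8% | 0.218/0.46 = 0.47 |

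The percentages match those printed. Baseline GI means of 1.35 and 1.37 lie in the protocol's moderate band, so there was room to fall. The detectable 0.20 units is 0.203/0.026 = 7.8 to 0.203/0.011 = 18.5 times the change in either arm.

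**3. Consistency of the tables.** The arm means give GI changes of 1.33 - 1.35 = -0.02 (tablet) and 1.34 - 1.37 = -0.03 (toothpaste), against -0.026 and -0.011 in Table 4. The toothpaste figure becomes 0.03/1.37 = 2.2%, and the order of the arms reverses. The Table 4 intervals imply paired-t p-values of about 0.55 and 0.70 for GI; the printed values are 0.765 and 0.936. A rank test might explain this, but none is stated. GI is nearly flat under either set of figures; with a change of 0.03, the ratio in step 2 is 0.203/0.03 = 6.8.

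**4. Power if the whole observed GI change were lost.** SD of change = CI half-width / 2.093 x sqrt(20) = 0.193 (tablet) and 0.126 (toothpaste). Pooled, this is sqrt((0.193² + 0.126²)/2) = 0.163. With 20 per arm, two-sided 0.05, noncentral t:
- loss of 0.011: d = 0.011/0.163 = 0.07, power about 5%;
- loss of 0.026: d = 0.026/0.163 = 0.16, power about 8%.

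On two-week scores instead of changes (SD 0.224), power is about 5% to 6%. The same check for PI changes (SD 0.434) gives 34% to 36%.

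**5. What the GI comparison does exclude.**
- From the two-week means and SDs: 1.33 - 1.34 = -0.01; SE = 0.224 x sqrt(2/20) = 0.0707; 95% CI = -0.01 ± 2.024 x 0.0707 = -0.15 to 0.13.
- As printed in Table 3: -0.167 to 0.083. This interval is centred at -0.042, whereas the printed difference is -0.06 and the means differ by -0.01.
- Difference in changes: -0.026 - (-0.011) = -0.015, 95% CI -0.12 to 0.09.

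The upper limits, 0.08 to 0.13, bound the tablet disadvantage.

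**The case against.** The protocol openly chooses two recognised indices, so keeping GI primary could be called a design preference, and the missing margin is a gap that also affects PI. Both remarks are fair. They do not supply a reason to expect GI to respond in two weeks, or to read its non-significance as equal efficacy.

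Several stronger readings are tempting, and the documents do not support them:

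- **That 14 days is too short because the protocol cites 21.** The sentence reads "Due to its quick formation in a matter of 21 days, untouched biofilm left on tooth surfaces". It concerns plaque left undisturbed, whereas these subjects brush at least twice a day. The documents give no response time for GI under brushing, so they show neither that 14 days is too few nor that a later examination would be enough.
- **That the GI result is uninformative.** Baseline GI near 1.36 on a 0 to 3 scale could have moved either way, and the intervals do exclude a sizeable worsening on tablets.
- **That two-week GI is merely baseline carried forward.** The implied baseline-to-two-week correlations are 0.72 and 0.86 for GI, but also 0.59 and 0.69 for PI. Correlation is not insensitivity; it makes change scores more precise.
- **That duration alone explains the flat GI.** The unchanged routine, the common new brush and the absence of an entry threshold may all contribute.
- **That PI alone supplies assay sensitivity.** There is no negative control, both arms changed brush, and the tablet PI interval also includes zero. The case for PI as primary is that it measures the stated objective.

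**Conclusion.** The point holds as limited here. GI does not measure the stated objective, its two-week timing is unjustified, and it moved by about 1% to 2% of baseline in both arms. With 80% power only for about 0.20 units and no margin, a non-significant GI difference excludes a tablet disadvantage above about 0.08 to 0.13 units and no more. That bound is several times the change seen in either arm, so it cannot show that an effect was preserved.

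The figures rest on three assumptions. The SDs come from the reported results, because the plan gives none. The Table 4 intervals are taken as paired-t intervals with 20 per arm. The power in step 4 treats the observed change as the true response, so it is an illustration and not a design calculation. The discrepancies among Tables 2 to 4 limit precision but do not alter the conclusion.

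**What to change.** - In Sections 5, 6a and 17, name PI as the primary endpoint and GI as secondary. Because results are already in the document, state that this reclassification is post hoc.
- Whether or not GI is reclassified, report the between-arm GI difference with its 95% CI, and state in Section 17 that a non-significant two-week GI result will not be used to conclude equal efficacy on gingivitis.
- Reconcile the GI means, differences, intervals and p-values in Tables 2 to 4, and name the test behind each p-value.

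The cost is wording, a disclosed post hoc change and a check of the tables against the data. The real downside is that the trial gives up a primary claim on gingivitis.

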- 9. "Amazon.com: Colgate Anywhere Travel Toothpaste Tablets with Fluoride ..." *Amazon*, https://www.amazon.com/Colgate-Anywhere-Toothpaste-Anti-Cavity-Refillable/dp/B08KQMC5MJ.
- 10. "Cavity Protection Toothpaste: Colgate®." *Cavity Protection Toothpaste* | *Colgate*®, https://www.colgate.com/en-us/products/toothpaste/cc-cavity-protection.
- 11. Moslehzadeh, Kaban. "Quigely Hein Index (modified). *Malmo University*. 27 Apr. 2016, https://www.mah.se/CAPP/Methods-and-Indices/Oral-Hygiene-Indices/Quigely-Hein-Index-modified/
- 12. Wilkins, Esther M., et al. *Clinical Practice of the Dental Hygienist*. 12th ed., Wolters Kluwer, 2017, pp. 372, 400.
- 13. *Amazon.com : Colgate Slim Soft Gliding Tips Toothbrush, extra soft ...* (n.d.). Retrieved August 30, 2022, from https://www.amazon.com/Colgate-Gliding-Toothbrush-Extra-Compact/dp/B07NXDWX78

Schedule of Events

	VISIT 1 (Day/Week/Month)	VISIT 2 (Day/Week/Month)
Informed Consent	X	
Baseline Oral Examination (GI & PI)	X	
Distribution of Product	X	
Post 2-Week Oral Examination (GI & PI)		X
Survey Distribution		X
Weight		
Vital Signs		
Oximetry		
Spirometry		

RESULTS

Table 1. Summary of Gender and Age for Subjects Who Completed the Two-Week Clinical Study

	Nun	Age			
Dentifrice	Male	Female	Total	Mean	Range
Sodium Fluoride Toothpaste1	8	12	20	25	18-36
Sodium Fluoride Toothpaste Tablet2	6	14	20	25	19-30

Table 2. Summary of the Baseline Loe-Silness Gingival Index Scores and Quigley-Hein Plaque Index Scores

	Dentifrice	N	Baseline (Mean±SD)		p-value	95% Confidence Interval	
Parameter				Mean Difference		Lower	Upper
Gingivitis	Toothpaste Tablet	20	1.35±0.26	-0.08	0.47	-0.19	0.13
	Conventional Dentifrice	20	1.37±0.24				
Plaque	Toothpaste Tablet	20	2.80±0.58	0.06	0.665	-0.36	0.38
	Conventional Dentifrice	20	2.78±0.46				

Table 3. Summary of the two-week Loe-Silness Gingival Index Scores and Quigley-Hein Plaque Index Scores

Parameter	Dentifrice	N	Two-Week (Mean±SD)		p-value	95% Confidence Interval	
				Mean Difference		Lower	Upper
Gingivitis	Toothpaste Tablet	20	1.33±0.26	-0.06	0.37	-0.167	0.083
	Conventional Dentifrice	20	1.34±0.18				
Plaque	Toothpaste Tablet	20	2.59±0.49	0.08	0.579	-0.25	0.417
	Conventional Dentifrice	20	2.56±0.48				

Table 4. Summary of Within Group Analysis of Loe-Silness Gingival Index and Quigley-Hein Plaque Index Scores

						95% Confidence Interval	
Parameter	Dentifrice	N	Mean Difference	Percent Reduction	p-value	Lower	Upper

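### Table 4's unplanned within-arm plaque reductions cannot be attributed to either dentifrice, because brush and brushing instructions also changed in both arms; efficacy conclusions should rest on the between-arm contrast

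*Combined protocol and SAP*

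**What the plan says.** Section 6b gives every subject a new study brush: "New toothbrushes will be used for both groups—Colgate Slim Soft Gliding Tips Toothbrush, Extra Soft, Compact Head". It then sets brushing time and frequency in each arm. For tablets: "Subjects will gently chew on the tablet to dissolve it and will brush for two minutes at least twice a day". For conventional paste: "Group A will use Colgate Cavity Protection toothpaste and brush at least twice a day for two minutes". The same section also says: "Subjects will be instructed to use their normal oral hygiene routine throughout a 2-week timeline".

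Section 6c places baseline scoring directly after consent: "The examiner will then perform an oral examination to provide an evaluation of plaque and gingival" indexes. The Schedule of Events puts consent, the baseline examination and "Distribution of Product X" in the Visit 1 column; the next examination is at two weeks. No run-in is described, and no arm goes without a test dentifrice.

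Section 17 plans an independent-sample t-test between the groups, or a Mann-Whitney test if the scores are not normal. It plans no within-arm test. The results nevertheless include "Table 4. Summary of Within Group Analysis of Loe-Silness Gingival Index and Quigley-Hein Plaque Index Scores", with a mean change, percent reduction, p-value and interval for each dentifrice. The conventional plaque row, for example, reads "0.218 7.8 0.035 -0.391 -0.045" (the first figure is a fall).

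**The concern.** Visit 1 appears to capture each subject on their own brush, dentifrice and habits. Visit 2 captures the same subject on a new brush, an assigned dentifrice and brushing instructions, and knowing that a second examination was coming. The dentifrice is one part of that package, and a before-and-after difference within one arm cannot isolate it.

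Table 4 labels the change by dentifrice, calls it a percent reduction and tests it against zero. All the between-arm p-values are large (0.47 and 0.665 at baseline; 0.37 and 0.579 at two weeks), so the two plaque p-values in Table 4 are the ones a reader will notice. No caveat accompanies them.

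Section 5 says the results are to support a decision whether to recommend the tablets, and Section 12 expects they may influence the public to switch. An unqualified plaque reduction of 8% beside the tablet's name could be carried into that decision as a product effect.

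**Working it through.** **Inputs**

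| Plaque | Tablet | Conventional | Source |
|---|---|---|---|
| Baseline mean | 2.80 | 2.78 | Table 2 |
| Two-week mean | 2.59 | 2.56 | Table 3 |
| Change | -0.224 | -0.218 | Table 4 |
| 95% CI of change | -0.453 to 0.005 | -0.391 to -0.045 | Table 4 |
| Stated p | 0.017 | 0.035 | Table 4 |

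There are 20 subjects per arm.

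**1. Reproduce the percent reductions.** Change divided by baseline mean: 0.224/2.80 = 8.0% and 0.218/2.78 = 7.8%. Both match Table 4.

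**2. Standard error of each change.** CI half-width divided by t(0.975, 19 df) = 2.093.
- Tablet: (0.005 + 0.453)/2 = 0.229; 0.229/2.093 = 0.109.
- Conventional: (0.391 - 0.045)/2 = 0.173; 0.173/2.093 = 0.083.

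**3. Between-arm difference in change**, in which the shared brush and instructions cancel.
- Difference: -0.224 - (-0.218) = -0.006.
- SE: √(0.1094² + 0.0827²) = 0.137.
- 95% CI with t(0.975, 38 df) = 2.024: -0.006 ± 2.024 × 0.137, that is -0.284 to 0.272; p = 0.97. Welch degrees of freedom (35.4) give the same interval.

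**4. Consistency of the plaque rows.** A paired t-test implied by each interval:
- Tablet: t = 0.224/0.1094 = 2.05, p about 0.055. The stated p is 0.017, although the interval includes zero.
- Conventional: t = 0.218/0.0827 = 2.64, p about 0.016. The stated p is 0.035.

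A rank test could explain such mismatches, but Table 4 names no test.

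**5. Consistency with Tables 2 and 3.**
- Tablet: 2.80 - 2.59 = 0.21 (7.5%). With two-decimal rounding the most this could be is 2.805 - 2.585 = 0.22, so 0.224 is out of reach.
- Conventional: 2.78 - 2.56 = 0.22, compatible with 0.218.
- On these means the difference in change is -0.21 + 0.22 = +0.01, the opposite sign to step 3.

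**6. Does the conflict in step 4 change the answer?** Suppose instead that the p-values come from paired t-tests and the intervals are wrong. The t values for p = 0.017 and 0.035 on 19 df are 2.616 and 2.271, so the SEs are 0.224/2.616 = 0.086 and 0.218/2.271 = 0.096. The SE of the difference is √(0.0856² + 0.0960²) = 0.129, and the interval is -0.006 ± 2.024 × 0.129, about -0.27 to 0.25. The conclusion is the same.

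**The case against.** The strongest reply is that no planned inference is affected. Section 5's objective is comparative, the primary endpoint is a between-product comparison, and Section 17 tests only that. Giving both arms one brush and the same brushing time and frequency is ordinary standardization, and it cancels under randomization. This stands. For the same reason, the lack of a run-in or of an arm without dentifrice is not a defect for the trial's own question, and a run-in could not help a cohort that has already reported.

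It is also true that no sentence credits the fall to a product. Table 4 is titled as a within-group analysis, its percent column is simple arithmetic, and its dentifrice column serves as the arm label. The point is therefore about what the table can support, not about a false statement in it. The tests remain unplanned and unqualified.

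Three stronger readings are tempting, and the documents support none of them.
- A reader might note that the conventional arm shows 0.218/0.224 = 97% of the tablet fall and infer that 97% of it is due to brush and instructions. Two equally effective dentifrices would produce the same pattern. The ratio is also imprecise: the interval for the difference extends further on each side than the whole 0.224 fall.
- A reader might add regression to the mean. Section 7 sets no minimum plaque or gingival score, so subjects were not selected for high values.
- A reader might infer that the design cannot address whether the products perform alike. A randomized parallel comparison can address that; the limit here is precision.

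Two facts are less firm than they look. That the brush followed baseline scoring is inferred from the visit layout, since the distribution row does not name it. How far brushing habits changed is unknown, because prior habits are not recorded and Section 6b also refers to the subject's normal routine.

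**Conclusion.** The point holds as a limit on Table 4. The within-arm plaque falls of 0.224 and 0.218 cannot be attributed to the tablet or to the paste, and the shares due to brush, instructions, observation and dentifrice are not identifiable from this design. That does not show that the dentifrices contributed nothing. The randomized between-arm comparison is unbiased in this respect.

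The relevant estimate is a difference in plaque change of about -0.006 (95% CI -0.28 to 0.27). The 0.28 half-width exceeds either arm's whole fall, so the data neither separate the products nor establish that they are equal.

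This rests on three assumptions: that the Table 4 intervals are t-based on 20 subjects per arm, that the arms are independent, and that the new brush and instructions came after baseline scoring. The interval is provisional because the tablet row it uses is internally inconsistent.

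**What to change.** 1. Check the tablet plaque row against the subject-level data before keeping any of its values: p = 0.017 against an interval that includes zero, and 0.224 against the 0.21 implied by Tables 2 and 3. Check the conventional row's p-value at the same time, and name the test used.
2. In Table 4, remove the within-arm p-values and stop presenting percent reductions as efficacy results. Keep each arm's mean change and interval as description, with a note that both arms changed brush and received brushing instructions.
3. Add the between-arm difference in change with its 95% CI, recomputed from subject data, and draw efficacy conclusions only from between-arm contrasts.
4. Reconcile the two statements in Section 6b on normal routine and on instructed brushing time and frequency, and report what subjects were actually told.

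The cost is a few lines around Table 4 and a recalculation from existing data; Section 17 contains no within-arm test to remove. The downside is that the two nominally significant plaque p-values are no longer shown as product effects.

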8. RECRUITMENT AND RETENTION

A flyer will be posted on LLUSD dental hygiene board. Please see attachment.

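### The plan does not mask the examiner who grades GI and PI, so Visit 2 scores are open to bias if the examiner knows or learns the product

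*Combined protocol and SAP*

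**What the plan says.** Section 6c has subjects examined for PI and GI after consent. Two weeks later "a final assessment will be given by the same examiner done in the exact order and technique as the baseline test". It then adds: "At the end participants will receive a 10-item satisfaction survey". The Schedule of Events puts consent, the baseline examination and product distribution at Visit 1, in that order, and the second examination and the survey at Visit 2.

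On allocation, Section 6b says: "Randomization will be performed by using a randomization table that is generated by the statistician". It does not say who holds the table, who gives out product, or whether that person also examines.

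The arms are easy to tell apart. The control arm uses a conventional paste; in the tablet arm, "Subjects will gently chew on the tablet to dissolve it".

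Participation is described as "restricted only to a student consensus", and Section 8 gives the recruitment route: "A flyer will be posted on LLUSD dental hygiene board". Section 3 lists six people with the title "Senior Dental Hygiene student" and one dental hygiene faculty member. The examiner is not identified.

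Sections 5 and 17 predict no significant difference in GI or PI between the groups. Section 12 presents a finding of no difference as the benefit of the study.

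**The concern.** Using one examiner with a fixed order and technique is sound practice and is not the problem. It removes variation between examiners, but it does not stop an examiner who knows the product from scoring the arms differently. Randomisation does not prevent this either, because the scoring takes place after allocation.

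The exposure is the Visit 2 score, since the schedule lists baseline grading before product is given out. Subjects know which product they used and can mention it. As written, the plan would also let the examiner hand out product at Visit 1.

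Both endpoints involve judgement, to different degrees. GI grades depend on how marked the colour change and swelling appear; grade 1, for example, reads "1: Mild inflammation, slight change in color, slight edema, no bleeding on probing". Bleeding on probing helps to separate grades 1 and 2. PI is less exposed because most of its grades have spatial anchors.

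Bias could create a difference or hide one. Hiding one deserves attention because it would favour the result that the team predicts and describes as the benefit. The planned t-test or Mann-Whitney test cannot distinguish biased scoring from a true treatment effect or its absence.

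**Working it through.** **Check of the text.** Every available section was read for masking of the examiner, concealment of the table from the examiner, separation of dispensing from grading, and instructions to subjects not to disclose their product. None was found. Nor does any section say that the examiner knows the allocation. Some pages were removed before review and could not be checked.

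**Inputs.**
- GI is the total score over 18 surfaces (Section 6), with 20 subjects per arm (Section 6b).
- Table 3, GI: SDs 0.26 and 0.18, printed difference -0.06, 95% CI -0.167 to 0.083.
- Table 3, PI: printed difference 0.08, 95% CI -0.25 to 0.417.
- The number of PI sites is not stated. The range 12, 18 or 36 sites on the six teeth is assumed.
- The scoring errors below are assumptions, not estimates.

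**GI, effect of a scoring error.**
- One error of one grade on one surface in one subject: (1/18)/20 = 0.0028 on the arm mean, which is negligible.
- A same-direction error averaging one grade on one surface per subject throughout one arm: 20/(18 × 20) = 0.0556 on that arm's mean.
- Half-width of the printed CI: (0.083 + 0.167)/2 = 0.125, and 0.0556/0.125 = 44%.
- Half-width from the printed SDs: SE = √((0.26² + 0.18²)/20) = 0.0707; 2.024 × 0.0707 = 0.143; 0.0556/0.143 = 39%.

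**PI, same systematic error.** The half-width of the printed CI is (0.417 + 0.25)/2 = 0.3335.

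| Assumed sites | Shift in arm mean | Share of half-width |
|---|---|---|
| 12 | 1/12 = 0.083 | 25% |
| 18 | 1/18 = 0.056 | 17% |
| 36 | 1/36 = 0.028 | 8% |

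**Effect on the test.** The pooled two-week GI SD is √((0.26² + 0.18²)/2) = 0.224, so a shift of 0.056 is about 0.25 SD. For the two-sided t-test at 0.05 with 20 per arm (noncentral t, 38 df):
- With no true difference, a 0.25 SD shift raises the rejection rate from 5.0% to 12.0%.
- Section 17 states 80% power but gives no effect size or SD, so its sample size cannot be reproduced. Solving backwards, 20 per arm and 80% power imply a standardised difference of 0.909, or about 0.909 × 0.224 = 0.20 GI units. If a 0.25 SD shift works against such a true difference, power falls from 80% to 52.9%.

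**Effect on the printed intervals.** Moving the GI interval by 0.0556 in either direction gives -0.223 to 0.027 or -0.111 to 0.139. Moving the PI interval by the largest assumed shift, 0.083, gives -0.333 to 0.334 or -0.167 to 0.500. All four still include zero.

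**The case against.** The strongest reply is that the point rests on silence. The plan never says that the examiner knows the arm, and some pages could not be checked. This stands: the documents show a missing safeguard, not an unmasked examiner.

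The link between subjects and examiner is also inferred. The wording about students is unclear, and a notice board does not place subjects in the examiner's programme. Section 3 is not a complete list of those involved, because a statistician (Section 6b) and a supervising dentist (Section 11) appear elsewhere. Student researchers take consent at a reception desk (Section 9), so some tasks may already be separated from grading. All of this is fair. An acquaintance between examiner and subject is a possibility, and the concern does not depend on it: any examiner can be told the product by a subject or can be the one who gives it out.

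The illustration is open to criticism too. Nothing in the documents supports a uniform error in one arm. With no true difference, such an error would separate the arms, against the team's prediction. The Table 3 GI benchmark is itself inconsistent: the printed difference is -0.06, the printed means differ by 1.33 - 1.34 = -0.01, and the CI midpoint is (-0.167 + 0.083)/2 = -0.042. The assumed shifts also leave every interval including zero. These points limit what the figures show. They do not supply the missing safeguard, and an interval that still includes zero is little comfort when no difference is the conclusion sought.

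Finally, the survey comes last and cannot affect a score already recorded at that visit, so who handles it is a minor matter.

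**Conclusion.** The concern holds. Followed as written, the plan leaves both primary endpoints open to differential scoring at Visit 2, GI more than PI. The same-examiner rule does not address this.

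Whether bias occurred, in which direction and how large cannot be determined from the documents. The illustrative GI shift of 0.056 (39% to 44% of the CI half-width) assumes a systematic same-direction error in one arm. The PI figures (8% to 25%) also assume the number of sites. They show that a modest but consistent tendency would matter at this sample size, whereas isolated errors would not.

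This should be corrected. It does not show that the tabulated results are wrong, but it limits how firmly they support a conclusion of no difference unless masking is confirmed. Confidence is medium, because the plan is silent rather than explicit.

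**What to change.** **For the results already tabulated.** State whether the examiner was masked to product at Visit 2. If not, report unmasked assessment as a limitation on the conclusion of no difference. This costs one sentence.

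**For any further or repeat use of the plan, in Section 6c:**
- State that the examiner is masked to allocation at both visits.
- Have a different team member hold the assignments and give out product after baseline scoring is complete.
- Tell subjects not to mention their product to the examiner or bring it to the examination.
- Reveal allocation to the examiner only after all scores are entered.
- Keep the survey at the end, handled by someone other than the examiner.

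The cost is a small division of tasks among the seven people already listed in Section 3, with no added staff, visits or procedures. The rewrite cannot change scores already collected.
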